4.6 Early Discontinuation/Withdrawn from the Study

If a participant decides to withdraw from the study, the investigator may ask the participant who is withdrawing whether the participant wishes to provide continued follow-up and further data collection subsequent to their withdrawal from the interventional portion of the study.

Participants that undergo tick placement and discontinue study participation by the PI's wishes will continue to come to visits for subject safety assessments or may be asked to provide vital safety information over the phone. Attempts will be made to contact participants who are lost to follow up.

4.7 Repeat of Xenodiagnosis Procedure

All repeats of the xenodiagnosis procedure are optional.

Repeat of the xenodiagnosis procedure can be offered to participants in 3 situations:

- a. Participants in whom the xenodiagnosis procedure failed to recover at least 14 intact engorged ticks.
- b. Participants in whom the xenodiagnosis procedure is positive.
- c. Participants who have completed the study as acute EM or Lyme arthritis patients and are eligible to participate as *Patients with Lyme disease, post-therapy*.

For participants in whom at least 14 intact engorged ticks are not recovered, 1 additional xenodiagnosis procedure (placement of ticks) will be offered. This does not require re-enrollment. Based on our experience with the phase 1 study, we expect that this may occur in up to 50% of the placements. Xenodiagnostic procedure will not be offered to participants with acute erythema migrans, as they will have started antibiotic therapy at the time of the initial tick placement.

For participants in whom the xenodiagnosis procedure is positive, re-enrollment will likely be required, due to the time necessary for results from the testing of the xenodiagnostic ticks to be finalized, as participants will likely have completed the follow up phase of the study. The study procedures will be repeated as described above, including the skin biopsy (optional) and follow up visits.

Participants who completed the study as *Acute Erythema Migrans* or *Lyme Arthritis patients*, and are eligible to participate as *Patients with Lyme disease, post-therapy*, will be enrolled as part of the new patient group and a new study number will be assigned. The study procedures will be repeated as described above, including the skin biopsies (optional) and all follow up visits.

Therefore, the maximum number of xenodiagnosis procedures offered to a participant for each group and situation, and the expected time period for the procedures are described in the Table 1 below.

Table 1: Maximum Number of Xenodiagnosis Procedures to be Offered

Group	Description	Xenodiagnosis, initial	If xeno positive	Enroll as a new participant?	Total	Time period between first and last possible tick placement
1	Patients with Lyme disease, post-therapy	Up to 2	Up to 2	No	Up to 4	3-6 months
2	Patients with post-Lyme disease	Up to 2	Up to 2	No	Up to 4	3-6 months

	complaints at least 12 months from initial treatment					
3	Acute EM	1*	*	Yes, as Group 1	Up to 5 (1 as EM, up to 4 as post-therapy)	7-18 months
4	Lyme Arthritis	Up to 2	*	Yes, as Group 1	Up to 6 (2 as LA, up to 4 as post-therapy)	7-18 months
5	Healthy volunteers	Up to 2		No	Up to 2	2 weeks

* Repeat will not be offered, as patients will have received antibiotic therapy at this point and results would not be comparable.

The date of each visit will be determined by the date from each procedure. In case there is overlap of visits, visits may be combined. Participants will be followed until completion of the protocol from the time of the last xenodiagnosis procedure. Lyme serologies will be repeated if performed more than 2 months from the placement. Approximately 40 mL of blood will be drawn and a urine sample may be collected for storage for future study related research at the repeat Tick Placement visit if the repeat xenodiagnosis procedure is more than 21 days from the initial tick placement.

Research bloods (approximately 40 mL of blood) will be drawn at the repeat tick removal visit for future study related research.

- The tick placement site may be the same or a different site, depending on individual preferences.
- For participants repeating because of less than 14 engorged ticks recovered, the period between the tick placement procedures can be from the time of tick removal up to 3 months post tick removal, and up to 1 repeat may be offered for each planned round of xenodiagnosis to ensure adequate collection of ticks for testing.

Participants who are offered the procedure because of a previous positive xenodiagnosis do not need to meet entry criteria at the time of the repeat procedure. All participants must fail to meet any exclusion criteria at the time of tick placement.

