Participants who underwent xenodiagnosis included 10 patients with high C6 antibody levels, 10 patients with post-treatment Lyme disease syndrome (PTLDS), 5 patients with acute erythema migrans after completion of antibiotic therapy, one patient with erythema migrans on therapy (who also underwent xenodiagnosis after antibiotic therapy), and 10 healthy volunteers. Seven patients underwent more than one xenodiagnosis procedure.

As no previous protocol for xenodiagnosis with *I. scapularis* larva in humans existed, we developed a retention dressing using the LeFlap™ (Monarch Labs, Irvine, CA) dressing, which was modified for use with ticks. Participants enrolled early in the trial had fewer ticks feed successfully due to issues with the tick retention dressing that resulted in entrapment of the ticks in the adhesive.

After modifying the dressing by adding a foam ring to create a barrier between ticks and adhesive, we were more consistently able to get between 30 and 50% of ticks to feed successfully.

Xenodiagnosis was well tolerated. All participants successfully completed the tick placement and there were no withdrawals during the study. The most common AE was mild itching at the site, which was seen in 58% of participants, with a median duration of 3 days. Repeat of the xenodiagnosis procedure was similarly well tolerated, with mild itching at the site as the most common complaint. There were no serious AEs associated with the procedure. Although not a primary goal of this pilot study, we did find 2 participants that tested positive and 2 participants who tested indeterminate for the presence of *B. burgdorferi* in the xenodiagnostic ticks.

In this Phase 2 study, we plan to expand our study of xenodiagnosis for Lyme disease in humans. Xenodiagnostic evidence that *B. burgdorferi* survives in humans after antibiotic therapy may fundamentally change the approach to patients with persistent symptoms and provide physicians and researchers with a new tool with which to study the mechanisms of disease.

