If the Initial Visit and the Placement Visit do not occur together, the initial skin biopsy may be performed at either visit, accordingly to the preference of the participant and study personnel.

Xenodiagnosis

Between 25-30 larval ticks that have been aged and are known to be ready to attach will be placed (Figure 1). The area chosen for the placement will be as close as possible to the site of the previous EM, if possible. Ticks will not be attached to head, neck or genitalia. If necessary, body hair will be shaved at the site. The ticks will be placed inside the Creature Comforts II LeFlap™ dressing which has been modified for tick use with the addition of a foam inner layer. The LeFlap is a pre-assembled confinement dressing that is used with medical maggots. Participants will be requested to keep the dressing dry for the duration of the attachment. Participants will receive an instruction sheet with instructions regarding care of the dressing and a Diary Card. The subject will be asked to complete a diary card daily starting the date of placement of the ticks through 30 days after tick removal.

Figure 1: Feeding of *Ixodes* Larvae under LeFlap Dressing

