7 STUDY ANALYSIS

7.1 Sample Size Justification

This study is powered to detect difference in the positivity rate between symptomatic and asymptomatic individuals. Self-reported symptoms will be characterized using symptom scales, the SF-36v2 questionnaire and fatigue scales. We will use a composite score derived from the measurement to assign symptomatic and asymptomatic status to the participants.⁷⁹

While the majority of the patients with Lyme disease who were treated with antibiotic therapy were negative by xenodiagnosis in our Phase 1 study, the number of patients tested in each group was small and the upper limit of the 95% confidence interval of each proportion is relatively high (up to 46%). Also, an important caveat is that the number of tested xenodiagnostic ticks per participant in general was also small, and the number of engorged ticks that are tested for each individual is an important variable, as the more engorged ticks tested, the larger the probability of detecting a positive. For example, if the true sensitivity for a single engorged tick to detect the bacteria is 1/10 (based on results of the mice studies), then one would need to recover 14 engorged ticks to have 75% sensitivity and 22 fed ticks to have 90% sensitivity.

Based in our very preliminary data, the upper limit of the exact 95% confidence interval for the proportion of positive xenodiagnosis in symptomatic patients (10%) was 0.445. Table 2 shows the sample size needed for 80% power, with a Type I error rate of 0.05, assuming varying assumptions for the true prevalence rates for asymptomatics (p_1) and symptomatics (p_2). For example, with a total sample size of 86 individuals, there would be 80% power to detect a between-group difference in the positivity rate if the true prevalence is 5% or less in the non-symptomatics and at least 30% in the symptomatics, assuming equal numbers between the 2 groups, (43 non-symptomatics and 43 symptomatics).

Table 2: Sample Size Needed for 80% Power with a Type I Error Rate of 0.05, and Varying Assumptions for the True Prevalence Rates for Asymptomatics (p_1) and Symptomatics (p_2)

	$p_2 = 0.40$	$p_2 = 0.30$
$p_1 = 0.05$	54	86
$p_1 = 0.025$	46	68
$p_1 = 0.01$	42	60
$p_1 = 0$	40	56

Assuming a 10 to 20% rate of missing data due to failed screenings, assays or participant drop-out, we plan to recruit up to 100 individuals.

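### Expecting a shortfall below 14 ticks in up to 50% of placements is not supported as an upper limit by the protocol's own tick count and feeding rate, and no analysis uses the number of ticks tested

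*Combined protocol and SAP*

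**What the plan says.** - **Threshold and expected shortfall (section 4.7).** A repeat may be offered to "Participants in whom the xenodiagnosis procedure failed to recover at least 14 intact engorged ticks". On how often that will happen, citing Phase 1 experience: "we expect that this may occur in up to 50% of the placements". Repeats are optional, and this one is not offered to acute EM participants, who will already have started antibiotics.
- **Ticks placed (section 4.2, Xenodiagnosis).** "Between 25-30 larval ticks that have been aged and are known to be ready to attach will be placed".
- **Feeding rate (section 1).** Before the dressing was changed, yields were lower: "Participants enrolled early in the trial had fewer ticks feed successfully due to issues with the tick retention dressing". After the change, "we were more consistently able to get between 30 and 50% of ticks to feed successfully".
- **Where 14 comes from (section 7.1).** If a single engorged tick detects the organism with probability 1/10, a value taken from mouse studies, "one would need to recover 14 engorged ticks to have 75% sensitivity and 22 fed ticks to have 90% sensitivity". The same paragraph calls the number of engorged ticks tested an important variable.
- **Analysis (section 7.1).** Fisher's exact test is planned for two categorical variables, with t-tests and nonparametric methods for continuous ones. The number of ticks tested per person is not named in any analysis.

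**The concern.** Fourteen fed ticks out of 25 to 30 lies near or above the top of the feeding range that the protocol reports. One would then expect most placements to fall short, whereas section 4.7 puts the figure at no more than half.

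Three things depend on the yield:

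- **Detection probability varies between people.** It rises with the number of engorged ticks tested. If that number differs between symptomatic and asymptomatic participants, a difference in positivity can reflect tick yield, and a true difference can be masked. The repeat rule widens the spread: someone who recovers 13 ticks and accepts a repeat may end with far more tested ticks than someone who recovers 14 and has none.
- **Acute EM (N=40) is one of the two attempted positive controls in section 3.2 and gets no repeat.** Negatives from low-yield placements there say little about the method.
- **The shortfall rate sets how many untreated Lyme arthritis participants meet the low-yield condition in section 3.2**, which concerns the timing of treatment around a repeat. This review takes no view on that rule.

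**Working it through.** **Inputs.** Ticks placed n = 25 to 30 (section 4.2). Feeding probability p = 0.30 to 0.50 (section 1). Threshold 14 (section 4.7). Single-tick detection probability 0.10 (section 7.1). The documents give no derivation of the 50%, no Phase 1 tick numbers per placement and no distribution of fed ticks, so the 50% cannot be reproduced. It can only be compared with what these inputs give.

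**Step 1: the threshold.** With k ticks, sensitivity is 1 − 0.9^k. This gives 74.6% at k = 13, 77.1% at k = 14 and 90.2% at k = 22. The section 7.1 figures hold: 14 is the first count to reach 75%, and 22 reaches 90%.

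**Step 2: expected yield, no model needed.** 25 × 0.30 = 7.5 and 30 × 0.50 = 15. Feeding needed for 14: 14/25 = 56.0% and 14/30 = 46.7%. With 27 ticks, 50% feeding gives 13.5.

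**Step 3: probability of a shortfall.** Assume ticks feed independently, so the number fed is X ~ Binomial(n, p). P(X ≤ 13) is:

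| Ticks placed | 30% feeding | 40% | 45% | 50% |
|---|---|---|---|---|
| 25 | 99.4% | 92.2% | 81.7% | 65.5% |
| 26 | 99.1% | 89.2% | 76.2% | 57.8% |
| 27 | 98.6% | 85.5% | 70.1% | 50.0% |
| 28 | 97.9% | 81.3% | 63.6% | 42.5% |
| 30 | 96.0% | 71.5% | 50.3% | 29.2% |

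The feeding rate at which the shortfall equals 50% is 53.9% for 25 ticks (outside the reported range), 50.0% for 27, 48.2% for 28 and 45.1% for 30. With 25 or 26 ticks the shortfall exceeds 50% throughout the reported range. Averaged over 25 to 30 ticks and 30 to 50% feeding with equal weight (an assumption), it is 79%.

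**Step 4: relaxing independence.** With a beta-binomial and an assumed intra-placement correlation (ICC) of 0.05 to 0.30, the shortfall at 40% feeding is:

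| ICC | 25 ticks | 30 ticks |
|---|---|---|
| 0.05 | 82.7% | 64.5% |
| 0.10 | 77.3% | 62.0% |
| 0.20 | 71.2% | 59.8% |
| 0.30 | 67.7% | 58.9% |

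So clustering lowers the mid-range figure to about 59 to 83%, still above 50%. At ICC 0.30 the whole range, from 30 to 50% feeding, is about 45 to 80%.

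**Step 5: detection from one placement.** At 1/10 per tick with independent feeding, mean sensitivity is 1 − (1 − 0.1p)^n.

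- 25 ticks: 53.3% (p = 0.30), 64.0% (0.40), 72.3% (0.50)
- 30 ticks: 59.9%, 70.6%, 78.5%

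**Step 6: with a second placement.** If both placements are done, 1 − (1 − 0.1p)^(2n) runs from 1 − 0.97^50 = 78.2% to 1 − 0.95^60 = 95.4%.

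**Step 7: acute EM, no repeat.** At 40% feeding, 40 × 0.715 = 28.6 to 40 × 0.922 = 36.9, so about 29 to 37 of 40 would fall short. The 50% figure implies at most 20.

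**The case against.** **The figure is empirical and hedged.** Section 4.7 attributes it to Phase 1 and says only that it may occur. The feeding range in section 1 is loose narrative that could be a mean, a typical span or something else. Setting a model against data one cannot see is weak ground for replacing the number. This stands, and it is why showing the Phase 1 distribution is an acceptable remedy. It does not rescue 50% as a ceiling: the feeding range is also Phase 1 experience, earlier yields were lower, and section 4.7 counts only intact recovered ticks, which cannot exceed the number fed.

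**The ranges overlap.** With 27 to 30 ticks and feeding of about 45 to 50%, the shortfall is 29 to 50%. A reader might infer that the sections contradict each other. They do not: the stated figure is attainable, but only at the favourable end.

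**Independence is not stated in the protocol.** Correct. The percentages in step 3 depend on it, and clustering narrows the range. The mid-range conclusion survives every correlation tried.

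**The 75% is only an illustration.** A reader might infer that the trial's sensitivity is lower than claimed, or that the power calculation fails. The documents support neither. Section 7.1 gives 75% as a conditional example, claims no per-person sensitivity for the study, and does not use 75% in Table 2. The single-placement range of 53 to 79% also includes 75%.

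**Repeats mitigate.** Two placements give about 78 to 95%. That stands for those who have both, but not for acute EM participants or those who decline.

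**Supply.** A reader might infer that ticks or repeat visits are under-planned. The documents contain no supply plan built on 50%, and Table 1 already allows two initial placements in every group except acute EM.

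**EM caveats already exist.** Section 3.2 calls these groups an attempt and notes that skin cultures turn negative quickly on treatment. That is a separate limitation, which low tick yield adds to.

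**Conclusion.** The point holds in a limited form. On the protocol's own tick count and feeding rate, a shortfall in more than half of placements is likely: 71.5 to 92.2% at 40% feeding under independence, and about 59 to 83% with an assumed ICC of 0.05 to 0.30. A figure of 50% or less is reached only with 27 to 30 ticks and feeding near 45 to 50%, so it is optimistic as an upper limit without being impossible.

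At the illustrative 1/10 per tick, one placement gives mean sensitivity of about 53 to 79% (64 to 71% at 40% feeding), against the 75% benchmark tied to 14 ticks.

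The practical consequence lies in the analysis. Tick yield will vary between people and will often be below the protocol's own benchmark, yet no planned analysis uses it. Table 2 is unaffected. The result rests on reading 30 to 50% as the range of feeding rates to expect in this trial, on the correlation assumed, and on the mouse-based 1/10 for the sensitivity figures.

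**What to change.** 1. **Reconcile sections 1, 4.2 and 4.7.** Either restate the expected shortfall as likely above 50% (roughly 60 to 90% at mid-range feeding, with the independence or clustering assumption given), or replace it with the Phase 1 distribution of engorged ticks per placement and the number of ticks placed. The second is better if the data are to hand.
2. **Add tick number to the analysis in section 7.1.** Report positivity with the number of engorged ticks tested per person, by group, separating first placements from repeats. Keep Fisher's exact test, and prespecify a supporting symptomatic versus asymptomatic comparison that accounts for tick number. One option is a complementary log-log model with log(ticks tested) as offset, which matches the 1 − (1 − θ)^k reasoning already in section 7.1, where θ is the per-tick detection probability. If positives are too few to fit it, stratify by fewer than 14 versus 14 or more. Present acute EM negatives alongside their tick counts.

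The cost is a few sentences of text, plus one recorded count per placement and per person tested. The stated shortfall becomes less favourable. No change to the number of ticks placed or to the repeat rule is proposed.

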3.2 Inclusion Criteria

Criteria for the diagnosis and therapy for Lyme disease can be found at “The clinical assessment, treatment, and prevention of Lyme disease, human granulocytic anaplasmosis, and babesiosis: clinical practice guidelines by the Infectious Diseases Society of America”⁵.

Patients with Lyme disease, post-therapy (N=100)

1. Age 18 or older.
2. Lyme disease diagnosed in the previous 13 months, fulfilling the case definition of confirmed or probable Lyme disease by the US Centers for Disease Control and Prevention (CDC) <https://www.cdc.gov/nndss/conditions/lyme-disease/case-definition/2017/>.
3. Completion of 1 course of antibiotics at least 3 months and up to 12 months between the end of the therapy and the xenodiagnostic procedure.
4. Antibiotic treatment fulfills the Infectious Diseases Society of America guidelines for the recommended therapy for Lyme disease⁵.

Patients with post-Lyme disease complaints at least 12 months from initial treatment (N=40)

1. Age 18 or older.
2. Diagnosed with confirmed or probable Lyme disease fulfilling the case definition of Lyme disease by the CDC <https://www.cdc.gov/nndss/conditions/lyme-disease/case-definition/2017/>.
3. Received recommended antibiotic therapy for Lyme disease⁵ at least 12 months between the end of the initial antibiotic therapy and the xenodiagnostic procedure.
4. Persistent or recurrent symptoms that began or worsened within 6 months of the diagnosis and treatment for Lyme disease.

Acute EM (N=40)

1. Age 18 or older.
2. EM diagnosed by the study physician.
3. Receiving antibiotic therapy for Lyme disease for less than 48 hours.

Lyme Arthritis (N=40)

1. Age 18 or older.
2. Lyme arthritis⁵⁰ and have not received antibiotic therapy for the disease.

Healthy volunteers (N=20)

1. Age 18 or older.
2. No prior history of Lyme disease.
3. Negative whole cell enzyme-linked immunosorbent assay (ELISA) or C6-based antibody test for Lyme disease.

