Patients with recently diagnosed (acute) EM (within 48 hours of starting antibiotic therapy) and patients with untreated Lyme arthritis will be recruited in an attempt to increase the chances of finding a positive result by xenodiagnosis (an attempt of a “positive control”). While patients with acute untreated EM would be the best positive control group, it would be unethical to withhold therapy in these patients for the few days required for tick feeding, due to the risk of dissemination of the organism and possible morbidity. Patients with untreated Lyme arthritis will

be recruited to establish whether xenodiagnosis can be used to identify infection in late stage Lyme patients where the bacterium is known to be present. These patients have been infected for months and will not be harmed for delaying therapy for a few days. Lyme arthritis is a late manifestation of *B. burgdorferi* infection, and hematogenous dissemination already occurred at this late stage. Studies have shown that the presence or absence of previous antibiotic treatment is more predictive than the duration of untreated arthritis for the success of antibiotic therapy in Lyme arthritis.^{6,8,51-53} Similarly, patients who just started therapy for EM may still have live *Borrelia* in the skin and xenodiagnosis may be able to recover the bacteria (but culture of skin biopsies from patients with EM become negative very quickly - within one dose - on antibiotic therapy).

While treatment for Lyme disease will not be offered under this protocol, it may be available via different clinical research protocols or regular medical care at the study site. If not, treatment will be prescribed by the patient's primary care. For patients with untreated early Lyme disease (erythema migrans), antibiotics can be started at the same day of tick placement. For patients with untreated Lyme arthritis, antibiotics can be started after collection of xenodiagnostic ticks (usually 4-5 days, up to 7 days). For patients with Lyme arthritis, if less than 14 ticks fed successfully and if the participant agrees, antibiotic treatment can be delayed until after the repeat procedure (see Section 4.7).

Patients with acute EM and untreated Lyme arthritis will be able to re-enroll as Patients with Lyme disease, post-therapy. Therefore, in case of positive results, we will be able to compare between the procedures.

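### Untreated Lyme arthritis: the no-harm rationale in 3.2 covers a delay of days, but 3.2 and 4.7 together allow about 3 months without antibiotics

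*Combined protocol and SAP*

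**What the plan says.** Section 3.2 enrols 40 patients with Lyme arthritis who "have not received antibiotic therapy for the disease". On holding back treatment while ticks feed, it says: "These patients have been infected for months and will not be harmed for delaying therapy for a few days". For one procedure it gives the length: "antibiotics can be started after collection of xenodiagnostic ticks (usually 4-5 days, up to 7 days". It then adds an exception for participants in whom fewer than 14 ticks fed: "if the participant agrees, antibiotic treatment can be delayed until after the repeat procedure". The exception carries no number of days and refers to Section 4.7.

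Section 4.7 times a repeat for too few ticks by one rule for every group: "the period between the tick placement procedures can be from the time of tick removal up to 3 months post tick removal". Table 1 allows up to two procedures as a Lyme arthritis participant. Its interval for that row, 7-18 months, also spans later placements after re-enrolment in the post-therapy group.

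Section 4.3 schedules tick removal 4 to 6 days after placement and allows removal visits to continue to day 10.

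**The concern.** The justification and the permission are on different time scales. Section 3.2 speaks of days, and its usage shows what it means: for acute EM the same section calls it "unethical to withhold therapy in these patients for the few days required for tick feeding", so the phrase refers to the feeding period. The exception then borrows its timing from a general rule that runs to 3 months. Most participants under that rule have no treatment waiting on the repeat. Those with untreated Lyme arthritis do.

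Followed as written, the rules let a known infection go without antibiotics for about 3 months on a rationale written for about a week. The stake is participant safety. This group lies outside the powered comparison of symptomatic and asymptomatic patients, so the primary inference is not affected.

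**Working it through.** **Is the repeat window untreated time for this group?** Three parts of the text say so.

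- Section 3.2 places treatment after the repeat.
- Section 4.7 applies the exclusion criteria at every tick placement. Exclusion 1 in Section 3.3 is worded as a negative; on its evident reading it bars antibiotics active against Lyme disease in the previous 3 months and excepts only acute EM. A Lyme arthritis participant treated after the first collection could then not have a repeat within the window.
- The Table 1 footnote treats results obtained after antibiotics as not comparable. In the Lyme arthritis row it is attached to a repeat after a positive result, so it supports the point only by analogy.

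**Length of the permitted interval.** Untreated interval = first collection + repeat window + second collection.

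Inputs:

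- Feeding time per collection: 4 days (4.3 minimum), 7 days (3.2 upper figure), 10 days (4.3 maximum).
- Repeat window: up to 3 months after tick removal (4.7). The protocol does not convert this to days. Assumption: 84 days (12 weeks) to 92 days (longest three calendar months; the shortest is 89).

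The plan's own figure for one procedure is up to 7 days. With the repeat placed at the end of the window:

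| Count | Sum | Days |
|---|---|---|
| Shortest feeding, 12 weeks | 4 + 84 + 4 | 92 |
| Shortest feeding, shortest calendar quarter | 4 + 89 + 4 | 97 |
| 7-day collections of 3.2, longest quarter | 7 + 92 + 7 | 106 |
| Longest feeding, 12 weeks | 10 + 84 + 10 | 104 |
| Longest feeding, longest quarter | 10 + 92 + 10 | 112 |

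Feeding alone accounts for 4 + 4 = 8 to 10 + 10 = 20 days. The exception for a repeat plainly provides for this, so it is not counted against the plan. The remaining 84 to 92 days are the window, when no ticks are feeding.

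**How many could be offered it.** Section 4.7 expects too few ticks in up to 50% of placements. If that rate held in this group, up to 0.5 × 40 = 20 participants could be offered a repeat. The documents do not say how late repeats would fall.

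**Secondary mismatch.** One collection takes up to 7 days in 3.2 but may run to day 10 in 4.3.

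**The case against.** The strongest counter-argument is that 3 months was never meant for this group. Table 1 gives healthy volunteers 2 weeks between first and last possible placement. Their only possible second placement is the repeat for too few ticks, so the one row that isolates this repeat shows a short interval. The acute EM and Lyme arthritis rows both show 7-18 months, although only Lyme arthritis has a repeat before re-enrolment. This is fair evidence about intent, but it sets no limit for Lyme arthritis. The 2-week entry itself disagrees with the 3-month rule, and Section 4.7 makes general provision for repeats more than 21 days after the first placement.

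Second, no one is made to wait. Every repeat is optional, deferral needs the participant's agreement, and treatment is given elsewhere: "While treatment for Lyme disease will not be offered under this protocol". All of this stands, and it limits the claim to what is permitted. It does not supply a rationale for a delay of months.

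Third, 3.2 offers more than the few-days sentence. It says dissemination has already occurred at this stage and cites studies in which "the presence or absence of previous antibiotic treatment is more predictive than the duration of untreated arthritis" for the success of treatment. That compares two predictors; it does not say that a delay of months is harmless, and the section's own conclusion remains a few days. The documents neither show harm from a longer delay nor exclude it.

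Fourth, Section 5 is organised by study procedure, and the consent pages were removed. Nothing is inferred here about what participants are told.

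**Conclusion.** The concern holds, and the text must be corrected. Sections 3.2 and 4.7 together permit about 3 months without antibiotics in untreated Lyme arthritis: 92 to 112 days from first placement to second collection when the repeat is placed at the end of the window. The only no-harm conclusion in the protocol is for a few days. With the 7-day collections of 3.2 and the longest calendar quarter the total is 106 days, about 15 times the 7-day figure (106 / 7 = 15.1).

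The lower total of 92 uses the shortest feeding times; with collections to day 10 the range is 104 to 112. The result rests on reading 3 months as 84 to 92 days and on the cross-reference from 3.2 to 4.7 carrying the general window with it. What is shown is a gap between a rule and its stated safety rationale, not a demonstrated harm and not a forecast of actual delays.

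**What to change.** Reconcile the Lyme arthritis text in Section 3.2, the collection period in 4.3, and the repeat rules and Table 1 in 4.7, so that the permitted delay of treatment and the rationale given for it agree. Table 1 should show the interval for the Lyme arthritis repeat separately from the post-therapy placements, and its 2-week entry for healthy volunteers should be squared with the general window. The 7-day and 10-day figures for one collection should also be made consistent. Section 5 should address delay of treatment as a risk. How this is resolved is for the sponsor's clinicians and the IRB; no interval is proposed here.

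The cost is protocol wording. Depending on the resolution, some repeats may be forgone, leaving those participants with fewer than 14 ticks. At the per-tick sensitivity of 1/10 assumed in Section 7.1, 14 ticks give 1 - 0.9^14 = 77.1% and 13 give 1 - 0.9^13 = 74.6%, so these participants would fall below the 75% sensitivity that Section 7.1 links to 14 ticks.
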